Patients meeting National Comprehensive Cancer Network guidelines for referral for genetic services will be identified using the screening tool developed and implemented in the EPIC EHR (Study Aim 1). The primary care providers (PCPs) of eligible patients will be notified of their patient's eligibility one week prior to patients being notified of the recommendation for genetic services. Patients will then be referred to participate in standard of care genetic services, with the clinical procedures depending on the study arm to which the clinic was randomized: enhanced standard of care or patient-directed standard of care.

Patients meeting criteria will be notified of the recommendation through the patient portal (i.e. MyChart). Those who do not have MyChart will be notified by mail. Those notifications will be followed by standard scheduling procedures. Patients who do not have MyChart will be asked to sign up for MyChart when they are contacted. Those who were not actively using MyChart will be provided with a refresher on the use of MyChart since this project focuses on using this tool to deliver genetic services more effectively.

Patients who do not have access to the internet or are unwilling or able to use MyChart will be directed to in person genetic counseling services. A waiver of consent will be requested to track the individuals who are not able to participate through MyChart, but they will not be asked to complete study questionnaires.

Study Arms – Clinic Randomized

Enhanced Standard of Care

This arm is referred to as enhanced since clinical decision support (CDS) tools are used to identify patients meeting guidelines rather than relying solely on provider identification of patients. Patients in this arm will have an in-person or telephone pre-test genetic counseling visit. Pre-test counseling includes review of the family history, risk assessment, discussion of the purpose of genetic testing and possible outcomes, implications for insurance coverage, costs, and assessment of psychosocial needs.

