Aim 2 analyses will address the dimensions of Reach, Effectiveness, Adoption, and Implementation from our conceptual framework. For Effectiveness, we will be testing for equivalence between study arms in uptake of genetic testing. We will check randomization by comparing demographic characteristics between patients in the two arms. Any characteristic(s) that are significantly different will be controlled for in the multivariable analysis. We will examine descriptive statistics, and will use Fisher's Exact test with a two-sided 0.05 significance level for univariate comparison of proportions to examine the association between study arm and uptake of genetic testing. We will next build multilevel multivariable logistic regression models to examine the effect of study arm on the outcome controlling for clinic-level (clinic type, patient volume, patient composition, number of providers), provider-level (specialty, years in practice, gender), and patient-level (e.g., sociodemographic, clinical) variables. We will examine the intra-class correlation (ICC) by clinic and provider. If a significant ICC is observed, the regression models will be extended to include random effects for clinic or provider, and fit using software for generalized mixed models. Covariates will be included in models if significant in unadjusted analyses. For Reach, using the multivariable regression models with interaction terms, we will examine whether the effects of study arm on uptake of genetic testing is modified by race/ethnicity or rurality. For Adoption, we will examine the proportions of providers and patients who access educational resources and with referrals, and whether this differs by population subgroup. For Implementation, we will assess responses to patient portal messages and completion of study workflows. Statistical significance will be assessed as $p < 0.05$; SAS 9.4 and/or Stata 15.1 will be used for analysis.

Aim 2 Sample Size

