Sample size for Aim 2 was calculated using PASS 15 based on an equivalence test for the difference of two proportions in a cluster-randomized design. Sample sizes of 480 in the patient-directed arm and 480 in enhanced standard of care arm, which were obtained by sampling 32 clusters (clinics) with 15 participants each and 16 clusters (clinics) with 30 participants each, respectively, achieve 80% power to detect equivalence. The margin of equivalence, given in terms of the difference between proportions, extends from -0.10 to 0.10. The calculations assume Likelihood Score Tests (Farrington & Manning) were used with an ICC of 0.05, and a significance level of 0.05. We believe that this is likely an overestimate of ICC based on our prior work. This sample size is sufficient for a multilevel multivariable regression analysis and achieves >95% power to detect a small effect size (0.02) attributable to 1 independent variable using an F-Test with an alpha of 0.05, adjusted for an additional 20 independent variables. To examine effect modification, sample size is calculated based on logistic regression of a binary response variable (Y) on a binary independent variable (X) and a binary confounder variable (Z). A sample size of 1,710 observations achieves 80% power at a 0.05 significance level to detect the X-Z interaction odds ratio of 1.5, using a two-sided Wald test. We will therefore enroll 1,920 patients in the Aim 2 trial to allow for about 10% attrition.

Aim 3 Analysis

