Aim 3 analysis will follow analytic procedures to address the dimension of Effectiveness from our conceptual framework. For comprehension, concordance between patient responses and information from genetic counselors' notes will be scored. We will test bivariate relationships between the outcome variables and study arm using Student's t-test or the nonparametric Wilcoxon rank-sum test between continuous variables, and chi-square test (or Fisher's exact test if small cell counts) for categorical data. We will examine distributions for continuous outcomes and transform the data if skewed. Procedures for building multilevel multivariable linear (continuous outcomes) or logistic (binary outcomes) regression models are described above. Regression models extended to include random effects for clinic or provider will be fit using software for linear mixed models for continuous outcomes and generalized linear mixed models for categorical outcomes. As with Aim 2, we will examine effect modification by testing for significant interactions between variables in regression models.

Aim 3 Sample Size

We estimate a sample size of 1,100 for a multilevel multivariable regression analysis with >90% power to detect a small effect size (0.02) attributable to 2 independent variables using an F-Test with an alpha of 0.05 using PASS 15 Software. The variables tested are adjusted for an additional 20 independent variables. To examine effect modification sample size is calculated based on logistic regression of a binary response variable (Y) on a binary independent variable (X) and a binary confounder variable (Z) with a sample size of 1,710 observations achieves 80% power at a 0.05 significance level to detect the X-Z interaction odds ratio of 1.5. Calculations assume that a two-sided Wald test is used.

IRB_00123563

Created: 6/5/2019 3:01
PM

IRB_00123563

- Request for Waiver of Consent

PI: [name]

Submitted: 3/5/2019

Title: Broadening the Reach, Impact, and
Delivery of Genetic Services**Request for Waiver or Alteration of Consent***** Requested Waivers**

Date Created	Type of Request	Purpose of Waiver Request
View 3/18/2019	Waiver of Informed Consent	Waiver of consent for chart review without patient contact

IRB_00123563

Created: 6/5/2019 3:01 PM

PI: [name]

Submitted: 3/5/2019

IRB_00123563

IRB Smart Form

Title: Broadening the Reach, Impact, and Delivery of Genetic Services

Request for Waiver or Alteration of Consent

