IRB_00123563

- Consent Process

PI: [name]

Submitted: 3/5/2019

Title: Broadening the Reach, Impact, and Delivery of Genetic Services

Consent Process

1. The following investigators and internal staff will obtain consent (as indicated on the Study Location and Sponsors Page):

[name]	University of Utah
[name]	University of Utah
[name]	University of Utah
[name]	University of Utah
[name]	University of Utah
[name]	University of Utah
[name]	University of Utah
[name]	University of Utah
[name]	University of Utah
[name]	University of Utah
[name]	University of Utah
[name]	University of Utah

List by name, role, and affiliation any others who will obtain consent (e.g. [name], Co-Investigator, etc.).

[name], [name]-study coordinator

[name], [name], [name]-genetic counseling assistant(s)

[name], Co-I, senior genetic counselor

HCI Genetic Counseling Shared Resource (GCSR) Team:

[name]

[name]

[name]

[name]

[name]

All are certified, licensed genetic counselors who will conduct all genetic counseling following the standard FCAC clinical practices.

2. Describe the location(s) where consent will be obtained.

Consent will be obtained electronically via the web-based patient portal

3. Describe the consent process(es), including the timing of consent. Describe whether there is a waiting period between the consent process and obtaining consent from the participant (i.e., any time between informing participants and actually obtaining consent).

Patients who receive genetic services, whether or not they decide to test, will be sent the consent cover letter via patient portal inviting them to participate in the research procedures, with a link to an online questionnaire. The consent cover letter will be sent 4 weeks after genetic test results are returned for those who decide to test and about 8 weeks after participation in pre-test genetic counseling services for those who decide not to test. If no response is received to the

first message, after 1 week another message in the patient portal will be sent. If still no response up to 3 phone calls will be made.

4. Describe what measures will be taken to minimize the possibility of coercion or undue influence.

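### Aim 3 intervals can be too narrow if outcomes vary by genetic counselor, because the models allow random effects only for clinic or provider

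*Combined protocol and SAP*

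**What the plan says.** In section 4 (Study Information), item 9, Aim 2 Analysis, the plan states: "We will examine the intra-class correlation (ICC) by clinic and provider". Random effects follow only if an ICC is significant. The provider-level covariates are specialty, years in practice and gender, and the number of providers is a clinic-level variable. The term is not defined, but it reads as the primary care provider. The Aim 3 Analysis repeats the two levels: "Regression models extended to include random effects for clinic or provider will be fit using software for linear mixed models" for continuous outcomes, with the generalized equivalent for categorical ones. No counselor term, counselor ICC or related sensitivity analysis appears.

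Section 8 (Resources and Responsibilities), item 1, assigns counseling at Utah to one shared resource. Consent Process, item 1, lists its team: "All are certified, licensed genetic counselors who will conduct all genetic counseling following the standard FCAC clinical practices".

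Item 6 of section 4 describes the arms. For enhanced care: "Patients in this arm will have an in-person or telephone pre-test genetic counseling visit". A counselor also returns every result in that arm. In the patient-directed arm, pre-test education and negative results come through the portal. Counselors review all results, telephone those that are pathogenic or uncertain, and are available on request.

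**The concern.** The counselor is a level of delivery that the plan does not model, and exposure to it differs by arm. If one counselor sees patients from several enhanced clinics, those patients' outcomes may be correlated across clinics. A clinic effect treats clinics as independent, and a primary care provider effect does no better.

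The outcomes most open to this come from the questionnaires: experience with counseling, recall, comprehension, decision regret, distress and risk perceptions. Comprehension is also scored against the counselors' own notes, so counselor variation can enter through the measurement. The standard error of the arm difference would then be understated even if the clinic effect were always fitted.

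**Working it through.** **Inputs from the documents**
- Aim 3 Sample Size: 1,100 patients, effect size 0.02 (read here as Cohen's f²), "attributable to 2 independent variables using an F-Test with an alpha of 0.05 using PASS 15 Software"; a further 20 covariates enter the model.
- Aim 2 Sample Size: "sampling 32 clusters (clinics) with 15 participants each and 16 clusters (clinics) with 30 participants each", patient-directed and enhanced respectively, with clinic ICC 0.05. I carry these clinic counts and this ICC over to Aim 3.
- Continuing review created December 2023: 237 + 98 = 335 questionnaire completers.

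**Assumptions, because the documents give no figure**
- Equal arms (550 or 167.5 patients each) and outcome variance 1.
- 10 counselors in all, about five per health system, each serving several enhanced clinics.
- Counselor share *s* of the variance: 0.01, 0.02 or 0.05.
- No counselor effect in the patient-directed arm (relaxed in step 5).

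**1. The plan's own figure.** Noncentral F with λ = 0.02 × 1,100 = 22 and df 2 and 1,100 − 23 = 1,077 gives 99.1% power. The stated figure of more than 90% is therefore true; 636 patients would suffice for 90%. As described, the calculation has no clustering term at any level.

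**2. Variance of the arm difference with clinic modelled and no counselor effect, 1,100 patients.**
V₀ = (0.05/16 + 0.95/550) + (0.05/32 + 0.95/550) = 0.00485 + 0.00329 = 0.00814.

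**3. Add counselors.** The enhanced-arm mean gains *s*/10. The ratio of true to reported standard error is R = √(1 + (*s*/10)/V₀), and the actual type I error is 2 × (1 − Φ(1.96/R)).

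| Share *s* | Added variance | R | Type I error |
|---|---|---|---|
| 0 | 0 | 1.00 | 5.0% |
| 0.01 | 0.001 | 1.06 | 6.4% |
| 0.02 | 0.002 | 1.12 | 7.9% |
| 0.05 | 0.005 | 1.27 | 12.3% |

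Taking the share out of the patient-level variance changes the last figure to 12.2%.

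**4. At 335 completers.** V₀ = 0.05/16 + 0.05/32 + 2 × 0.95/167.5 = 0.0160. R is 1.03, 1.06 and 1.15, and type I error is 5.7%, 6.5% and 8.7%. The counselor term is unchanged, but patient-level noise is larger, so the inflation is smaller.

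**5. Contact in the patient-directed arm.** If a fraction *f* of those patients share the same counselor effects, the added variance shrinks by (1 − *f*)². At 1,100 patients:
- *s* = 0.02: 6.4% at *f* = 0.3 and 5.7% at *f* = 0.5.
- *s* = 0.05: 8.6% at *f* = 0.3 and 6.8% at *f* = 0.5.

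**6. Fewer counselors.** With five in all, 1,100 patients and *f* = 0, the three shares give about 8%, 11% and 19%.

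**7. Simulation.** With 5,000 replicates, counselors crossed with clinics within system and a Welch test on clinic means, type I error was 6.6%, 7.9% and 11% at 1,100, and 5.6%, 6.5% and 7.8% at 335. It was 4.1–5.0% with no counselor effect. In a further simulation at 1,100 patients, a partially nested counselor random effect brought clinic-only rates of 7.6% and 11.5% (shares 0.02 and 0.05) back to about 6%, with almost no change when the counselor variance was zero.

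**The case against.** A reader might infer that the Aim 3 error bars are too narrow as a matter of fact. The documents do not support that. They give no counselor ICC, and counseling follows standard clinic practice, which would tend to reduce differences between counselors. At a share of zero there is no inflation.

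The team size is also weak evidence. The Utah list has five entries, with a senior genetic counselor listed separately. It comes from the consent section of the 2019 application, and the continuing reviews record later staff changes. NYU's counselors are not described in the available text. That each counselor serves several clinics is an inference from one shared team and 16 enhanced clinics in the calculation.

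It is tempting to say that the effect does not cancel between arms. Counselors also work in the patient-directed arm, so it may partly cancel (step 5). For the assumed shares and team size, the main figures are therefore closer to an upper bound.

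The outcomes at issue come from questionnaires, and 335 people had completed one by the last review. There the simulated 5.6% is only about two Monte Carlo standard errors (0.3 points each) above 5%.

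The plan also has more direct causes of narrow intervals: clinic effects depend on a significant ICC, and the bivariate Aim 3 tests ignore clustering.

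Finally, a reader might infer a false finding of equivalence. Section 1 hypothesises equivalent adherence, but the Aim 3 Analysis sets no equivalence margin, and adherence is not the outcome closest to the counselor.

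All of this limits the size and the certainty. None of it puts a counselor level into the models, and repairing the clinic-level problems would not add one.

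**Conclusion.** The omission is documented; its effect is conditional. If outcomes vary by counselor and counselors serve several clinics, the clinic and provider effects cannot absorb that variance, and Aim 3 intervals for counselor-sensitive outcomes can be too narrow. Under the stated assumptions, a nominal 5% test runs at about 6.4% to 12% at the planned 1,100 patients and about 5.7% to 8.7% at 335 completers, for shares of 0.01 to 0.05. The inflation is nil at a share of zero, smaller where the patient-directed arm shares counselor effects, and larger with fewer counselors. This is a cheap improvement, not a demonstrated error in the results, and it ranks behind the conditional ICC rule and the unclustered bivariate tests.

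**What to change.** - Define the provider level, and record the genetic counselor for each counseled patient. State in advance which contact counts if the pre-test and results counselors differ.
- In the Aim 3 models for counselor-sensitive questionnaire outcomes, fit a clinic random effect whether or not the ICC is significant.
- Add a partially nested counselor random effect: zero for patients with no counselor contact, and applied to counseled patients in either arm. Use small-sample degrees of freedom.
- If that model is unstable with few counselors, report it at minimum as a prespecified sensitivity analysis.
- For Aim 2 uptake, use it as a sensitivity analysis only, because patients who were never counseled have no counselor.

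The cost is slightly wider intervals, an imprecise counselor variance estimate when counselors are few, and one added data field. Counselors' notes are already used to score comprehension, so the source may be at hand. However, the data lists in the waiver requests name the primary care provider and no counselor identifier, so they would need an entry. No new patient contact is required.

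### Clinics are randomised, but the arm tests ignore clinic, or allow for it only if the ICC proves significant

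*Combined protocol and SAP*

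**What the plan says.** The Study Purposes and Objectives (item 6) and Aim 2 put randomisation at clinic level. The Aim 2 Sample Size section uses a cluster-randomised equivalence test with margin ±0.10 and 480 patients per arm, arranged as "32 clusters (clinics) with 15 participants each and 16 clusters (clinics) with 30 participants each". It adds: "The calculations assume Likelihood Score Tests (Farrington & Manning) were used with an ICC of 0.05", and then: "We believe that this is likely an overestimate of ICC based on our prior work".

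The Aim 2 Analysis section (Study Information, item 9) states the hypothesis: "we will be testing for equivalence between study arms in uptake of genetic testing". For the unadjusted comparison the investigators "will use Fisher's Exact test with a two-sided 0.05 significance level for univariate comparison of proportions to examine the association between study arm" and uptake. The adjusted analysis follows: "We will next build multilevel multivariable logistic regression models to examine the effect of study arm". Random effects are conditional: "If a significant ICC is observed, the regression models will be extended to include random effects for clinic or provider".

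The Aim 3 Analysis section names patient-level t, Wilcoxon, chi-square or Fisher tests for the arm comparisons and refers back to the Aim 2 procedure for building its models.

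**The concern.** The models are called multilevel, but a model that has to be extended to include random effects does not start with them. Three problems follow.

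- The only arm test named for Aim 2 treats patients as independent.
- A clinic effect enters the model only after a significance test. A non-significant ICC is not evidence of a zero ICC, and the test is weakest at the small ICCs the sponsor thinks likely.
- The wording is clinic or provider, so even a significant ICC does not guarantee a clinic effect.

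Nothing in the available text accounts for clinic unconditionally or names the analysis that decides equivalence. If an unclustered test is used for inference, it finds differences too often. If an unclustered interval is used, it declares equivalence too often. The second error matters more here, because equivalence is the hypothesis.

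**Working it through.** **Inputs from the plan.** 32 clinics × 15 and 16 clinics × 30 (480 per arm, N=960); margin ±0.10; planning ICC 0.05; Fisher two-sided at 0.05; significance at p<0.05.

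**Assumed.** Uptake 20% and 30%; ICC 0.01 and 0.02, to illustrate the sponsor's view that 0.05 is too high; gate = Pearson heterogeneity test within arms on 48 − 2 = 46 df at 0.05; equivalence = 90% interval inside ±0.10; equal clinic sizes within arm; no covariates.

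**1. The plan's 80% power.** This cannot be checked outright, because no reference uptake is given. At ICC 0.05 the design effects, 1 + (m − 1) × ICC, are 1 + 14 × 0.05 = 1.70 and 1 + 29 × 0.05 = 2.45. With two one-sided tests at 0.05 and uptake 0.16, SE = √[0.16 × 0.84 × (1.70 + 2.45)/480] = 0.0341. Power = 2Φ(0.10/0.0341 − 1.645) − 1, about 80%. The same formula gives 52% at uptake 0.30. The stated figure is therefore consistent with clustering being allowed for, at uptake near 16%.

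**2. Closed-form error when clustering is ignored.** Let D be the mean of the two design effects. A nominal 5% two-sided z-test has size 2[1 − Φ(1.96/√D)]. An unclustered one-sided equivalence test at the margin has size 1 − Φ(1.645/√D).

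| ICC | Design effects | D | Difference test | False equivalence |
|---|---|---|---|---|
| 0.01 | 1.14, 1.29 | 1.215 | 7.5% | 6.8% |
| 0.02 | 1.28, 1.58 | 1.43 | 10.1% | 8.4% |
| 0.05 | 1.70, 2.45 | 2.075 | 17.4% | 12.7% |

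**3. Simulation of the plan as written.** Beta-binomial clinics, 20,000 trials per cell, N=960. When the gate fires, a clinic-level Welch test and interval are used; otherwise a pooled z-test and an unclustered interval. False equivalence is taken at a true 10-point difference. Nominal error is 5%.

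| | ICC 0.01 | ICC 0.02 | ICC 0.05 |
|---|---|---|---|
| Fisher, type I error | 6.6-6.7% | 8.8-9.0% | 15.5-16.0% |
| Unclustered interval, false equivalence | 6.4-6.8% | 8.3-8.6% | 11.7-13.1% |
| Gate fires | 22-23% | 49-50% | 94-95% |
| Gated, type I error | 6.5-6.7% | 6.5-6.7% | 5.3-5.5% |
| Gated, false equivalence | 5.6-6.0% | 5.8-6.1% | 4.5-5.5% |

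Fisher falls slightly below the z-test in step 2 because it is conservative.

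**4. The gate with fitted mixed models, closer to the plan's wording.** Logistic regression is replaced by a random-intercept model (Wald z) only when the clinic variance is significant. Three gate tests were tried, at uptake 16%, 30% and 50%, with 4,000 trials per cell. Type I error is 6.2-7.1%, 6.7-8.0% and 5.8-7.8% at the three ICCs. The gate opens in 11-23%, 32-51% and 85-96% of trials.

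**5. Always accounting for clinic.** A clinic-level Welch t gives type I error of 4.8-5.2% and false equivalence of 4.3-5.4% over ICC 0 to 0.05. An always-fitted random intercept at ICC 0.01 to 0.05 gives 5.6-6.5% with Wald z and 5.0-5.8% with t on 46 df (3,000 trials per cell, Monte Carlo SE about 0.4 points).

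**6. Full enrolment.** If all 1,920 patients come from the same 48 clinics (30 or 60 each, assumed), Fisher's error is 9.2-9.6%, 14.2% and 26%. The gated analysis of step 3 gives 6.7-6.8%, 5.6-5.7% and 5.0-5.3%.

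**The case against.** The best defence is that Fisher was never meant to decide. It is called univariate, it sits beside the descriptive statistics, and the regression models come next. On that reading the relevant figure is the gated model's, and its excess false equivalence is about one point or none. Fisher's excess rejections would also count against the sponsor's own hypothesis. Always fitting a random intercept with a plain Wald z test still runs at about 6%, so part of the gain comes from the degrees of freedom and not from dropping the gate. The planned clinic-level covariates could lower the residual ICC. Item 9 asks only for a summary, and the full protocol cited on the opening page was not available.

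Most of this stands as a limit on size. The larger figures apply only if an unclustered analysis is used for inference, and no Aim 3 calculation was done. It does not remove the defect. The conditional random effect is a stated rule, not an omitted detail, and the text neither labels Fisher descriptive nor says which analysis decides.

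A further objection is that cluster-adjusted power at ICC 0.05 is well below 80% for uptake of 20% or more. That is not a cost of the change: in simulation the gated and always-adjusted analyses have nearly the same equivalence power there (68.2% against 67.8% at 20% uptake, 49.4% against 49.0% at 30%).

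**Conclusion.** The concern holds and should be fixed. Making the clinic effect depend on a significant ICC is wrong for a clinic-randomised trial, and the named patient-level tests are invalid for inference on arm. The gated route costs about one to three points of type I error at ICC 0.01 to 0.02, depending on the gate and model, and at most about one point of false equivalence in the gated version simulated. An unclustered analysis costs far more at the plan's own ICC of 0.05: type I error near 16% for Fisher and false equivalence near 12-13%. The direction follows from the design alone. The exact figures rest on the assumed uptake, the lower ICCs, the form of the gate, the 90% interval rule and the absence of covariates.

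**What to change.** Amend the Aim 2 and Aim 3 analysis text as follows:

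- Account for clinic in every arm comparison, whatever the ICC test shows. Use a clinic-level analysis, or a clinic random intercept or GEE with small-sample degrees of freedom or correction.
- Add provider effects only in addition to clinic.
- Report the ICC descriptively, not as a gate.
- Label the patient-level Fisher, chi-square, t and Wilcoxon tests as descriptive.
- State that Aim 2 equivalence is judged on a cluster-adjusted risk-difference interval against ±0.10.

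This needs no new data and no larger sample. If the ICC is truly zero, the 90% interval widens from 0.0848 to 0.0865 at 20% uptake and from 0.0972 to 0.0991 at 30%. Equivalence power at N=960 then falls from 97.3% to 96.8% and from 92.0% to 91.0%. If the ICC is not zero, the adjusted interval is wider than the unclustered one by roughly √D: about 10% at ICC 0.01 (√1.215) and 20% at 0.02 (√1.43). At ICC 0.05 and 20% uptake it is 0.125 against 0.085. That extra width is the clustering the sample size calculation already assumes.
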